1. STUDY OBJECTIVES/HYPOTHESIS

We hypothesize that low levels of fitness and MVPA result in impaired metabolic function in adolescents. For this pilot study, we will quantify variations in metabolic characteristics using a 2 x 2 cross-sectional study design, stratified by bodyweight (normal vs overweight/obese) and physical activity (sedentary vs. active). Our goal is to identify metabolic factors that influence the energy balance system to directly inform interventions designed to prevent or reduce the prevalence of pediatric obesity.

Aim 1: To quantify the independent effects of physical inactivity and obesity on metabolic responses at rest, after a meal, and during exercise using indirect calorimetry.

Aim 2: To determine whether physical activity level impacts appetite control independent of obesity status via metabolic function.

Aim 3: To explore the hormonal and neurocognitive mechanisms of appetite control.

2. RATIONALE

At the most basic level, obesity is the result of a chronic energy surplus within the energy balance system. However, an assortment of physiological, psychological, and environmental factors are related to energy intake and expenditure, resulting in highly variable individual responses to identical intervention strategies [1, 2]. For example, a recent rigorous 10-month weight loss study observed a 5.6% average reduction in body weight, yet individual weight change ranged from a 22% weight loss to a 4% weight gain [3]. Physiologically, differences in energy metabolism likely explain much of this variation [4, 5], and identifying those individuals metabolically at risk for obesity or resistant to traditional weight loss strategies is a ‘key challenge’ of obesity researchers [6]. Thus, there is a critical need to identify metabolic factors that influence the energy balance system in order to develop effective interventions to treat obesity or prevent its occurrence. This project will clarify the relationship between physical activity, obesity status, and appetite control in adolescents.

3. STUDY DESIGN

The proposed pilot study consists of a 2 x 2 cross-sectional study design (Table 1), which will maximize statistical power despite a small sample size. Inclusion/exclusion criteria for MVPA and body weight are based on established criteria from governmental agencies and clinical practice.

4. TARGET STUDY POPULATION SPECIFICS

Participants will include 60 adolescent males (aged 14-18 years, Tanner stages III- IV), equally enrolled based on physical activity and body weight status (**Table 1**).

Table 1. Enrollment criteria based on physical activity and body weight status

Adolescents males (age 14-18 years & Tanner stages III- V)	Normal weight ($\geq 5^{\text{th}}$ to $< 75^{\text{th}}$ percentile)	Overweight/obese ($\geq 85^{\text{th}}$ to $< 99^{\text{th}}$ percentile) ⁴¹
Inactive (<30 min/day MVPA)	n= 15	n= 15
Active (>60 min/day MVPA) ⁴²	n= 15	n= 15

Inclusion Criteria

- Males (Tanner Stage III-IV), ages 14-18
- Weight stable ($\pm 5\%$ weight change) over the previous three months as assessed by self-report.
- BMI $\geq 5^{\text{th}}$ and $\leq 99^{\text{th}}$ percentile
- Physically healthy for exercise as assessed by self report Physical Activity Readiness Questionnaire (PAR-Q) for children.
- For fMRI testing, all participants must be right handed and must have normal or corrected to normal vision (as they will be viewing pictures in the fMRI procedure).

Exclusion Criteria

- History of restrained eating, eating disorders, bariatric surgery, or other significant medical diagnosis that could impact metabolism.
- Participants taking thyroid medications, beta blockers, or other stimulants (medications are known to affect physical activity level and metabolism).
- Due to fMRI procedure requirements, children with a history of Attention Deficit Hyperactivity Disorder (ADHD) or other diagnosed psychiatric issues will be excluded.

[figure not shown]
5. DATA COLLECTION

Data Collection Procedures

The study will include 4 visits and 1 home assessment window:

- Visit 1 - Orientation (Consent, Screening Questionnaires) at Don Chisholm
- Visit 2 - Clinic Measurements
 - Body composition, via dual energy X-ray absorptiometry (**DXA**)
 - Resting metabolic rate (RMR), via indirect calorimetry;
 - Metabolic responses to a meal, via thermic effect of feeding (**TEF**)
 - Subjective aspects of eating behavior using the Three Factor Eating Questionnaire (**TFEQ**) and Control of Eating Questionnaire (**CEQ**)
 - Appetite, via visual analogue scales (**VAS**) pre- and post a prepared fixed meal and hormones related to satiety and hunger (insulin, leptin, ghrelin, peptide YY, glucagon-like peptide-1) obtained during blood samples (**BLOOD**) from an indwelling catheter.
 - All measurements will occur at the CHLN (<9:00am) following an overnight fast.
- Home assessments - Data collected at home during a 14 day window
- Visit 3 - Fitness Test ($\text{VO}_{2\text{submax}}$ and $\text{VO}_{2\text{max}}$), grip strength, and DXA at Don Chisholm
- Visit 4 - fMRI at University of Kansas Medical Center

Please see Figure 1 below for schedule of measures:

\$150 compensation

Figure 1. Description of Measures:

Metabolic function.

- **Resting metabolic rate (RMR)** will be assessed via indirect calorimetry using a ventilated hood following an overnight dietary fast and ≥ 24 -hours since structured exercise (e.g. sports participation).
- **Thermic effect of feeding (TEF)** will measure the energy expenditure resulting from digestion following the fixed meal using the ventilated hood.
- **Submaximal oxygen consumption (fitness test) (VO_{2submax})** and **maximal oxygen consumption (VO_{2max})** will be assessed with a full-face mask with headgear via standard protocols using a treadmill. Measured during visit 3.

Body composition.

- Assessment of **body composition**, including fat mass, fat free mass, and visceral adipose tissue, will be completed using dual energy X-ray absorptiometry (DXA). All anthropometric measurements will be performed with the participant dressed in surgical scrubs and in bare feet. BMI (weight [kg]/height [m]²) will be calculated from the average of three height and weight measurements using a wall-mounted stadiometer and electronic scale and recorded to the nearest 0.1 cm and 0.1 kg, respectively.

Fixed/*Ad libitum* meals.

Appetite (see below) will be assessed following a fixed standard breakfast of 500 kcals. The fixed breakfast will be administered while the participant is in a fasted state (≥ 12 hours since last meal) and at least 24 hours since the last bout of exercise, and they will be asked to consume the meal within 15 minutes. Food intake (total kcals) will be assessed using an *ad libitum* pizza meal served three hours after the fixed meal. Participants will be instructed to eat until comfortably full and informed that they can request more of the pizza meal. Meals will be provided in 900 kcal portions, and each

plate of food will be weighed before and after serving, without the subjects' knowledge, and the amount consumed recorded. All meals will be served in a quiet dining room free from distractions located at the NWRC.

Appetite and Eating Behavior.

- Subjective assessment of hunger and palatability will be completed using self-rated visual analogue scales (VAS). Each scale consists of a 10 cm long line separating statements such as "not at all hungry" and "extremely hungry". Assessments will occur prior to the fixed meal, and every fifteen minutes for the first hour and every thirty minutes for the next two hours.
- Perceptions of dietary restraint, disinhibition, and hunger will be assessed prior to the fixed meal using the Three Factor Eating Questionnaire (TFEQ). The Control of Eating Questionnaire (CEQ) will be used to assess hunger, fullness, cravings, the desire to eat certain foods, and the ability to resist urges to eat. Assessed at visit 2.
- Blood samples obtained from an (insulin, leptin, ghrelin, peptide YY, glucagon-like peptide-1). Blood will be drawn at the following approximate times: -15 min (x2), 15 min, 45 min, 60 min, 90 min, 120 min, 180 min. Due to the number of blood draws, for participant safety and comfort a flexible, vacutainer accessible catheter will be placed by a registered nurse (who will also perform all blood draws). A total of 32 mL (1.08 oz) of blood will be drawn.

Lifestyle Assessment.

- Energy intake will be assessed using two methods: 1) objectively, as measured by amount of kcals consumed during an ad libitum meal (see above, section Fixed/Ad libitum meals), and 2) subjectively, assessed via interviewer-administered dietary recalls. Three dietary recalls will occur on randomly selected non-consecutive days over each two-week treatment condition (including at least one weekend day) to minimize preparation that could bias recall by the participants. All interviews will be conducted over the telephone, will ask about all foods consumed over the previous 24 hours using a multi-pass approach, and energy intake will be calculated using the Nutrient Data System for Research software (NDSR Version 2014).
- Energy expenditure will be estimated using an arm-based monitor (Sensewear™), which calculates energy expenditure using tri-axial accelerometry and measures of heat flux, galvanic skin response, skin temperature, and near-body ambient temperature. Assessed continually (day and night) over the 14 day home assessment period.
- Sedentary behavior will be assessed using a leg-mounted triaxial accelerometer with inclinometer (ActivPal™) which classifies time spent in sedentary, upright, and stepping activities. Assessed continually (day and night) over the 14 day home assessment period.
We will assess MVPA using a wrist-worn activity triaxial accelerometer (Actigraph GT9X Link™) which quantifies time spent in light activity and MVPA. Assessed continually (day and night) over the 14 day home assessment period.

SmartPhone prompts to assess cravings, anticipation of eating, and hunger

The SmartIntake™ smartphone app will be used as a photo-based ecological momentary assessment (EMA).

- **Craving:** We will use a single-item craving prompt to assess current food craving level: “Please rate on a scale from 0-100 the extent to which you agree with the statement: I am craving food.”
- **Anticipation of eating:** We will use a single item from Nijs et al (2007) General Food Craving-State Questionnaire to assess anticipation of eating: “Eating something tasty would feel wonderful.” We have chosen this prompt because it is agnostic as to the rationale for anticipating eating.
- **Hunger:** We will assess pre-meal hunger to account for the temporal relationship between hunger and craving in deprived and non-deprived states (Cepeda-Benito et al., 2000). Although hunger is sometimes conceptualized as an aspect of craving, our purpose is to distinguish physical hunger from craving to avoid confounds. We will use an adapted prompt from Goldschmidt et al (2014) “Please rate the extent to which you agree: I feel physically hungry, on a scale from 0-100, with 0 being not hungry, 100 being extremely hungry.”

fMRI Procedures.

- The fMRI study visit will take place at visit 4. Children will be met at the Hoglund Brain Imaging Center, part of the University of Kansas Medical Center, for the fMRI portion of the study. This visit to Hoglund will take approximately 1.25 hours. Children will take complete a computized behavioral food-rating task which asks the child to rate sixty food images on how the food tastes, how much the child would like to eat the food, and how healthy is the food. Then the child will complete a food-decision task while in the MRI. The child will see a picture of a food on the screen, and will choose which foods he/she would prefer to eat. Stimuli include items often consumed by children, and were selected to include a wide range of tastiness and healthiness attributes (for example, apple, broccoli, asparagus, glazed donut, French fries and marshmallows). This test will measure how the brain responds to making decisions about food. All food pictures are high-resolution (72 d.p.i.) color images with a size of 300x300 pixels. The stimulus presentation and behavioral response collection will be controlled by Presentation software (Neurobehavioral System).
- Additional questionnaires collected at this visit include Monetary choices, Flanker, and Consideration of future consequences.

Records to be kept

Data collected will be deidentified with a subject ID number. A linking list will be used, which will contain the subject ID, subject's name, gender, and date of birth. This log will only be accessible by the PI and the study team.

Secure Storage of Data

Consent statements and participant data in separate locked file cabinets so that individuals are not easily connected to the study results. All digital data will be stored on a firewall and password-protected project server at Children's Mercy Hospital. Data collected at the CMH Don Chisholm Center CMH will be analyzed and stored in secure shared drive at the Don Chisholm Center. Blood samples will be collected at Don Chisholm and shipped to Quest for processing. fMRI data will be collected at Hoglund Brain Imaging Center at KUMC and will be analyzed by KUMC study personnel at KUMC. This data will be deidentified, and will be sent back to the PI at CMH using secure file transfer.

SmartIntake App Data Security:

The app was developed and validated by [name] and colleagues at the Pennington Biomedical Research Center (PBRC) at Louisiana State University. The company Rapid Development Productions (RapDevPro) worked with [name] and colleagues to develop the app. By design, [name] and colleagues set up this app and secure data hosting platform to be available to researchers nationally and his team provides researchers data analysis services for the dietary intake data. Researchers can sign a contract/agreement to utilize the app for research purposes. No identifying information will be collected through the SmartIntake photo-EMA app.

SmartIntake is used to capture images of food and beverage intake before and after consumption. Photos are sent directly to a secured data server (see details of server security below) for analysis of dietary intake. Participants initiate each photo by opening the app, taking the picture, and then submitting the picture through the app. The app sends a reminder email 15 minutes after submission of the first photo to remind participants to submit their post-consumption photo. The app sends photos to the secured server by email, thus an email address is required to send the photos. Participants will be provided a secured email address that does not contain or link to any identifying formation, such as their names, etc, that the app can use to send the images. When images are sent to the server, the email address is stripped from the images before they are stored; thus all data stored on the PBRC server is deidentified. The app does not utilize, store, or transfer info from other mobile phone data sources including contacts or geolocation.

To minimize the risk of capturing identified data in the photos, participants will receive a training. Participants will be told that they should never include pictures of other people or their surroundings (bar signs, etc) in their photos. We will emphasize that we have a responsibility to collect strong research data while protecting those around them from inadvertently being included in photos without their consent. Participants will be shown that once the photo is taken, it will be stored on their phone's photo app. We will show participants how to go into their photo app and delete the picture taken with SmartIntake. We will tell them they should do this immediately after sending the photo in SmartIntake.

Photo data stored on the secured PBRC server: The only data stored with photo images is the unique participant ID. Email address is stripped from the data before storage to the server. Thus, only non-identifying info is stored on the PBRC server for analysis. The server that the data is stored on is in the PBRC domain and requires PBRC user credentials

to access the files stored on that server. Only [name] and his staff who directly manage or analyze the app data have access to the files where the images are stored. All PBRC logins are required to have a password of 15 or more characters and must be changed on a regular basis.

NOTE: The photo image data collected by the SmartIntake app will NOT be transferred to CMH at any point. The study PI will receive the deidentified dietary intake data that will be transferred through the PBRC secured data transfer system.

6. STUDY DURATION/STUDY TIMELINE

Target start date is May 2017

Stage 2, recruitment and data collection, June- November 2017

Stage 3, data analysis and grant/manuscript development, December 2017- May 2018

Total study duration will be 1 year.

We anticipate 4-6 waves of enrollment, with each participant enrolled for 4 weeks. Following an orientation (visit 1) during which informed consent will be obtained, individuals will participate in a clinic measurement session (visit 2), a 14-day free-living lifestyle assessment period, a 2nd laboratory visit (visit 3) for an exercise testing session, and conclude with a fMRI assessment (visit 4) All laboratory activities will occur at the CCHLN research facility, and the fMRI will occur at KUMC Hoglund Brain Imaging Center.

7. STATISTICAL CONSIDERATIONS

Measures

- Primary measures: Metabolic function and body composition
- Secondary measure(s): Demographics, appetite, food cravings, and eating behaviors, lifestyle assessment, fMRI, energy intake

General Design Issues

The proposed pilot study consists of a 2 x 2 cross-sectional study design, which will maximize statistical power despite a small sample size. This pilot study will generate data needed for a larger study.

Sample size determination

As a pilot study, we will have resources to collect data from N=60 participants. We will use this data to determine power requirements for a larger study.

Data Analyses

Statistical significance for comparison between groups will be tested using analysis of variance (ANOVA) for continuous variables and chi-square tests for categorical variables. Statistical significance will be set at P<.05 (two-sided) for all analyses.

fMRI Analysis. We will estimate several general linear models (GLMs). All of the models allow for first-order auto regression and included six motion parameters,

constants, and linear time trends for each run as regressors-of-non-interest. A two-stage mixed-effects analysis will be performed in which the regression coefficients for each condition of interest will be tested across participants via t-tests. Two-tailed tests are used for all statistical analyses. We will perform multiple comparison corrections at the cluster level using Monte Carlo simulations with the AlphaSim program.

EMA-Food Craving Analysis. A regression model will test whether mean EMA ratings of anticipation (craving) and reward (pleasantness rating, ate more than intended, ate beyond satiety) are correlated with postprandial glucose surge and area under the curve for glucose following the standardized lab meal.

We will use a hierarchical mixed model to examine the nested association between EMA-measured craving, food pleasantness, and overeating *within* eating episodes in free-living conditions. Pre-meal craving and within-meal pleasantness ratings will be used as predictors in models with overconsumption rating post-meal. Food photos will be used to distinguish HF from non-HF (fat/carb: 25%+/25%+; sweet/fat: 15-35%/30%+; salt-fat: 0.5-2.5%/10-35%) using the detailed NDSR nutrition data output we will receive from the app.

We will conduct a series of Pearson correlations to test whether craving and reward symptoms measured in the standardized meal and free-living conditions are significantly correlated.

We will use a linear regression model to test the degree to which anticipation (craving) and reward (food enjoyment, eating despite satiety) as measured using photo-EMA, and intensity of glucose surge during the standardized lab meal will be associated with % fat mass and visceral adipose tissue as measured using DXA.

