STATISTICAL ANALYSIS

Statistical significance for comparison between groups will be tested using analysis of variance (ANOVA) for continuous variables and chi-square tests for categorical variables. Statistical significance will be set at $P < .05$ (two-sided) for all analyses.

fMRI Analysis. We will estimate several general linear models (GLMs). All of the models allow for first-order auto regression and included six motion parameters, constants, and linear time trends for each run as regressors-of-non-interest. A two-stage mixed-effects analysis will be performed in which the regression coefficients for each condition of interest will be tested across participants via t-tests. Two-tailed tests are used for all statistical analyses. We will perform multiple comparison corrections at the cluster level using Monte Carlo simulations with the AlphaSim program.

EMA-Food Craving Analysis. A regression model will test whether mean EMA ratings of anticipation (craving) and reward (pleasantness rating, ate more than intended, ate beyond satiety) are correlated with postprandial glucose surge and area under the curve for glucose following the standardized lab meal.

We will use a hierarchical mixed model to examine the nested association between EMA-measured craving, food pleasantness, and overeating *within* eating episodes in free-living conditions. Pre-meal craving and within-meal pleasantness ratings will be used as predictors in models with overconsumption rating post-meal. Food photos will be used to distinguish HF from non-HF (fat/carb: 25%+/25%+; sweet/fat: 15-35%/30%+; salt-fat: 0.5-2.5%/10-35%) using the detailed NDSR nutrition data output we will receive from the app.

We will conduct a series of Pearson correlations to test whether craving and reward symptoms measured in the standardized meal and free-living conditions are significantly correlated.

We will use a linear regression model to test the degree to which anticipation (craving) and reward (food enjoyment, eating despite satiety) as measured using photo-EMA, and intensity of glucose surge during the standardized lab meal will be associated with % fat mass and visceral adipose tissue as measured using DXA.

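### The fMRI cluster correction by AlphaSim relies on Gaussian-shaped spatial correlation, and no cluster-forming threshold is stated, so its 5% error rate is at risk (not shown to be lost)

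*Protocol*

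**What the plan says.** The fMRI paragraph is the same in Protocol section 7 (Data Analyses) and in the SAP. First-level coefficients are "tested across participants via t-tests". On multiplicity it says "We will perform multiple comparison corrections at the cluster level", and the tool is named in both documents: "Monte Carlo simulations with the AlphaSim program" in the Protocol, "using Monte Carlo simulations with the AlphaSim program" in the SAP. The general error rate is "Statistical significance will be set at P<.05 (two-sided) for all analyses", and the fMRI paragraph adds "Two-tailed tests are used for all statistical analyses". No separate cluster-level error rate is given, so 5% is read across from the general statement.

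The only noise-correlation model named is "All of the models allow for first-order auto regression". It belongs to the models of the individual runs and describes correlation over time, not across the brain. Neither document gives a cluster-forming threshold, minimum cluster size, smoothing kernel, smoothness or spatial-autocorrelation estimate, voxel size, mask or search volume. Section 7 lists fMRI among the secondary measures.

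**The concern.** A cluster-size cutoff is only as good as the noise model behind it. AlphaSim simulates noise smoothed to one Gaussian width and takes the cluster size that chance rarely exceeds. This is a property of the named method; the documents do not describe it. If true correlation falls off more slowly than a Gaussian, neighbouring voxels at a distance exceed the threshold together more often than simulated, chance clusters grow, and the cutoff passes too many of them. The effect depends strongly on the cluster-forming threshold, which the plan leaves open.

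At stake are the brain regions reported for Aim 3. Section 7 also says the pilot is meant to inform a larger study, so a false region could be carried forward as a target.

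**Working it through.** **Figures in the plan.** There is no fMRI power, sample-size or cluster-size figure to reproduce. The usable numbers are alpha = 0.05, two-sided, and 60 participants ("we will have resources to collect data from N=60 participants"; 4 x 15 = 60 from Table 1). Everything else below is an assumption.

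**Assumptions of the main simulation.** Group z-maps; 3 mm voxels; whole-brain ellipsoid mask of 55,536 voxels; face-touching clusters; two-sided voxel thresholds of .01, .005 and .001; Gaussian smoothness F of 6 or 8 mm FWHM; 2,000 maps for calibration and 2,000 fresh maps for testing per setting. The 95% Monte Carlo margin at 5% is 1.96 x sqrt(.05 x .95/2000) = about 1.0 point, and somewhat more with calibration error.

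**Noise model.** Correlation at distance r is a x exp(-r²/(2b²)) + (1-a) x exp(-r/c). The share in the tail is 1-a. The Gaussian term equals exp(-2 ln2 x r²/F²).

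**Step 1: match one Gaussian width at lag 1.** Take F = 6 mm, a = 0.7, c = 12 mm. Correlation at 3 mm is 0.7 x 0.707 + 0.3 x 0.779 = 0.729. The matching width is 3 x sqrt(2 ln2 / -ln 0.729) = 6.28 mm. At 12 mm the fitted Gaussian has correlation exp(-2 ln2 x 144/6.28²) = 0.006, while the true one is 0.7 x 0.004 + 0.3 x 0.368 = 0.113. That gap is the mechanism.

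**Step 2: set the cutoff.** Simulate Gaussian noise at the fitted width and take the smallest extent k with P(largest cluster >= k) <= 0.05.

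**Step 3: apply k to fresh noise.** Entries are at voxel P<.01 / .005 / .001. The last column is the extent that would restore 5%.

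| F | Noise | k (voxels) | Family-wise error, % | k needed |
|---|---|---|---|---|
| 6 | Gaussian (control) | 26/19/10 | 5.0/5.2/5.7 | 26/20/11 |
| 6 | a=0.9, c=12 | 28/20/11 | 10.8/9.0/5.6 | 33/23/12 |
| 6 | a=0.7, c=12 | 30/22/12 | 33.8/22.4/10.2 | 51/33/14 |
| 6 | a=0.5, c=12 | 32/23/12 | 55.2/41.2/18.8 | 85/51/19 |
| 6 | a=0.7, c=18 | 34/24/13 | 36.1/28.1/11.2 | 73/43/17 |
| 8 | Gaussian (control) | 55/39/20 | 4.6/4.2/3.6 | 54/39/19 |
| 8 | a=0.9, c=12 | 52/37/19 | 11.4/8.8/6.5 | 62/42/21 |
| 8 | a=0.7, c=12 | 48/35/18 | 34.2/23.7/13.4 | 84/56/24 |
| 8 | a=0.5, c=12 | 46/33/17 | 51.3/39.1/20.4 | 112/71/28 |
| 8 | a=0.7, c=18 | 56/40/21 | 35.6/25.6/11.0 | 104/68/27 |

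The controls are about nominal. The long-tailed rows span 11-55%, 9-41% and 6-20%.

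**Step 4: vary the choices the plan leaves open.** A separate run used 1,000 maps per setting and a Gaussian SD of 4 mm (margin about 1.4 points near 5%).

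| Search volume, width matching | a=0.8, c=10 | a=0.6, c=14 |
|---|---|---|
| Whole brain, lag 1 | 18/12/9% | 42/28/15% |
| Whole brain, half-maximum | 12/8/4% | 21/14/8% |
| Sphere of 15 mm radius, lag 1 | 6/7/5% | 6/6/3% |

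Matching at half-maximum leaves 0.44 to 0.67 of the lag-1 error (4/9 to 12/18). In the same run a = 0.9 at P<.001 gave 4.6%, which extends the P<.001 range to about 5-20%. A third whole-brain run with 400 maps per setting gave 4/4/5% on Gaussian noise and 14/10/7%, 19/13/7% and 47/35/18% with 10%, 20% and 40% of the correlation in the tail, in line with the main results.

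**Step 5: price of a correct cutoff.** The ratio of extent needed to extent used runs from 12/11 = 1.1 to 28/17 = 1.6 at P<.001. At P<.01 it runs from 33/28 = 1.2 to 112/46 = 2.4 at 8 mm and 85/32 = 2.7 at 6 mm.

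**The case against.** The strongest reply is that the premise comes from outside the documents. Nothing describes the spatial correlation of these scans, so the simulation shows what would follow from a long tail, not that these data have one. This stands, and it limits the point to a risk.

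The size also rests on choices that the plan does not make. A whole-brain search with smoothness matched at lag 1 gives the large figures. Half-maximum matching cuts them to about half to two-thirds, and a small region brings them close to 5%. With a 10% tail at P<.001 the error is 4.6-6.5%, which is barely distinguishable from nominal. This stands too, and for that reason the figures are given as a range with the near-nominal cases beside it.

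The consequence is limited. fMRI is a secondary measure in a pilot, and Aim 3 is exploratory and also draws on hormone samples and behavioural tasks.

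A reader might infer that the reported brain regions will carry several times the stated error rate, or that Aim 3 as a whole is unsound. The documents support neither reading: they give no correlation, threshold or search volume from which an actual error rate could be computed, and the maps are only part of the evidence for Aim 3.

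The objection does not remove the core. The only multiplicity control named for fMRI depends on an unexamined spatial assumption and an unstated threshold. Under the same noise (a = 0.7, c = 12 mm), the plan as written allows an error of about 10-13% or about 34%, depending on a threshold chosen later.

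**Conclusion.** The point holds as a conditional weakness. The Gaussian-based cutoff keeps about 5% when its assumption is met and can exceed it when correlation has a longer tail. By how much depends on the tail, the voxel threshold, the search volume and the smoothness method, none of which the plan states. The upper ends of the ranges need half the correlation to lie in the tail, a whole-brain search and lag-1 matching. The main simulation used group maps with one stationary correlation, not 60 sets of subject maps. The primary measures are untouched. This is worth correcting because the remedy is cheap, not because an error has been shown.

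**What to change.** In the fMRI paragraph of both documents:

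- Replace AlphaSim with permutation cluster inference on the second-level maps: sign-flipping for one-sample tests, label permutation for group contrasts. This uses the data's own spatial correlation and needs no assumed shape. The alternative is to keep simulation but use the empirically estimated spatial autocorrelation.
- State one cluster-forming threshold, the search volume and the cluster-level error rate before the maps are analysed. If simulation is kept, also state how smoothness is estimated. P<.001 is a reasonable threshold, but permutation does not require it for error control.

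The cost is a text change, computing time and some sensitivity. No visit, scan or participant is added. If the tail is real, the clusters needed are about 1.1-1.6 times larger at P<.001 and may be more than twice as large at P<.01. With 15 participants per cell that loss should be acknowledged.

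### The within-episode EMA model does not name pre-meal hunger, which the protocol collects in order to keep hunger separate from craving

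*Protocol*

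**What the plan says.** Section 5 of the protocol (smartphone prompts, Hunger item) gives hunger an analytic role. It says "We will assess pre-meal hunger to account for the temporal relationship between hunger and craving in deprived and non-deprived states", and then: "Although hunger is sometimes conceptualized as an aspect of craving, our purpose is to distinguish physical hunger from craving to avoid confounds".

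Section 7 (EMA-Food Craving Analysis) plans a "hierarchical mixed model to examine the nested association between EMA-measured craving, food pleasantness, and overeating" at the level of the eating episode. Its terms are given in one sentence: "Pre-meal craving and within-meal pleasantness ratings will be used as predictors in models with overconsumption rating post-meal". The SAP repeats that sentence word for word.

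The other EMA analyses in Section 7 and the SAP do not name hunger either. The regression on post-meal glucose uses craving and "reward (pleasantness rating, ate more than intended, ate beyond satiety". The correlations between laboratory and free-living data concern craving and reward. The adiposity regression uses "anticipation (craving) and reward (food enjoyment, eating despite satiety) as measured using photo-EMA" together with the glucose surge. Neither document has a general rule for adding covariates.

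**The concern.** Section 5 treats hunger as a potential confounder of craving. Measuring a confounder does not remove it; it has to enter the model or be handled in some other stated way. The analysis text leaves that step out.

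If hunger is related to both craving and the overconsumption rating, the craving coefficient from the listed model mixes the two. If hunger raises the rating, craving is credited with an association that belongs to hunger. If hunger lowers it, a real craving association can be hidden or reversed. Both are possible, because the overeating items mentioned in Section 7 are judged against the boy's own intention and satiety, and a hungry boy could score higher or lower on them.

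Leaving the term open also allows the choice to be made after the craving result has been seen, with P<.05 applied to all analyses.

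**Working it through.** **Text check.** There is no figure in the plan to reproduce: N=60 is set by resources, with no power calculation. Set side by side:

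- Protocol Section 5: hunger is collected to allow for its link with craving and to keep the two apart.
- Protocol Section 7 and SAP, mixed model: predictors are craving and pleasantness; the outcome is the post-meal overconsumption rating; hunger is absent.
- Protocol Section 7 and SAP, remaining EMA models: hunger is absent.

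**Bias in the craving coefficient.** Suppose the rating depends on craving (c), pleasantness (p) and hunger (h), all standardised, with hunger coefficient b_h, and that correlations are the same within and between boys. If h is left out, the craving coefficient is shifted by

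bias = b_h × (r_ch − r_cp × r_hp) / (1 − r_cp²).

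The shift is zero only if b_h = 0 or if craving and hunger are uncorrelated given pleasantness. None of these inputs is in the documents, so every value below is an assumption.

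Main example: b_h = 0.3, r_ch = 0.5, r_cp = r_hp = 0.3. Bias = 0.3 × (0.5 − 0.09) / (1 − 0.09) = 0.3 × 0.41 / 0.91 = 0.135.

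Range:

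| b_h | r_ch | r_cp | r_hp | Bias |
|---|---|---|---|---|
| 0.1 | 0.3 | 0.5 | 0.5 | 0.1 × 0.05 / 0.75 = 0.007 |
| 0.3 | 0.5 | 0.3 | 0.3 | 0.135 |
| 0.3 | 0.5 | 0.5 | 0 | 0.3 × 0.5 / 0.75 = 0.200 |
| −0.3 | 0.5 | 0.3 | 0.3 | −0.135 |

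The last row shows masking: a true craving coefficient of 0.15 would be estimated at about 0.15 − 0.135 = 0.015.

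**Precision cost of adding hunger.** Before any offset from a smaller residual variance, the standard error of the craving coefficient is multiplied by 1/√(1 − ρ²), where ρ is the craving-hunger correlation given pleasantness:

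ρ = (r_ch − r_cp × r_hp) / √[(1 − r_cp²)(1 − r_hp²)].

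- Main example: ρ = 0.41 / 0.91 = 0.45; factor 1/√(1 − 0.203) = 1.12.
- ρ = 0.5: factor 1/√0.75 = 1.15.
- r_ch = 0.5, r_cp = 0.5, r_hp = 0: ρ = 0.5 / √0.75 = 0.58; factor 1/√(1 − 0.333) = 1.22.
- r_ch = 0.7, r_cp = 0.5, r_hp = 0: ρ = 0.7 / √0.75 = 0.81; factor 1/√(1 − 0.653) = 1.70.

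The raw correlation r_ch does not cap this cost. At r_ch = 0.5 it would give 1.15, while the third line gives 1.22.

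**The case against.** The strongest reply is that the analysis text is a summary. It speaks of models in the plural, never calls its predictor list complete, and leaves other things unplaced: the high-fat food classification is defined in the same paragraph without being assigned to a model, and no random-effects structure is given. A reader might infer that the investigators have decided to exclude hunger. The documents do not support that. They show only that hunger is not prespecified. The gap still matters here, because Section 5 gives confounding as the reason for measuring this particular variable.

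A second reply is that hunger may be part of craving, so adjusting for it would remove some of what is being studied. Section 5 acknowledges that view and then says the aim is to separate the two. Reporting the coefficient both ways serves either reading.

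A third is that Section 5's mention of deprived and non-deprived states could equally support stratification or a craving-by-hunger term. That stands: an additive covariate is the simplest option, not the only one the text allows. What the plan needs is a stated role for hunger.

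Finally, craving is a secondary measure, and free-living craving is not named in Aims 1 to 3. That limits the weight of the point but does not remove the mismatch.

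**Conclusion.** The concern holds as a mismatch between the stated purpose of the hunger prompt and the model that should use it. With the predictors as listed, the craving coefficient cannot be read as separate from hunger.

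The size and sign are unknown. The example of 0.135 and the spread from 0.007 to 0.200 in absolute value rest wholly on assumed correlations and hunger associations, and they are not bounds. A reader might infer that craving will be falsely significant, or that its association will be overstated. The documents support neither: they give no hunger association, no correlations and no expected number of rated episodes, and the bias could run either way or be negligible.

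The point should be addressed, but it is confined to a secondary analysis in a pilot. The primary comparisons of metabolic function and body composition are unaffected.

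**What to change.** In Section 7 and the SAP, add episode-level pre-meal hunger as a covariate in the within-episode mixed model, and state that the craving coefficient will be reported with and without it. If a within-boy reading is intended, craving, hunger and pleasantness can each be entered as a person-mean-centred value plus the person mean; this is optional.

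The change is cheap. Hunger is already being collected, so only the wording changes. The downside is the loss of precision for craving shown above, which becomes substantial if boys rate hunger and craving almost alike. Showing both estimates makes that loss visible.
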